10.2	Eve	ent Windows, Missed Assessments, Missed Sessions and Protocol Deviation	
Repo	orting		19
11.0	REGU	JLATORY	19
11.1	Inst	itutional Review Board (IRB)	19
11.2	Sub	ject Information and Consent	19
12.0	REFE	RENCES	20

tACS Study (HUM00208557)

13.0	APPENDIX	. 2	2
------	----------	-----	---

Title	Enhancing Neural Synchrony and Affective Cognitive Control in Bipolar Disorder using Personalized Transcranial Alternating Current Stimulation (tACS)
Study Design	The randomized, double-blind, sham-controlled, cross-over study will involve three sessions. The first session will involve a clinical interview, questionnaires, and EEG recording during a computerized task. The second and third sessions will involve tACS brain stimulation (or placebo stimulation) during a computerized task and EEG recording.
Study Duration	Enrollment duration: 12 months Subject follow-up duration: 1 month Estimated duration until study completion: 12 months
Study Center(s)	Single center
Aims	Aim #1: Evaluate the feasibility and acceptance of tACS among bipolar patients. Aim #2: Estimate the preliminary effects of personalizedtACS on theta-gamma phase-amplitude coupling (PAC) and cognitive control behavior in bipolar disorder (BD).
Number of Subjects	30
Disease/condition	Bipolar Disorder
Inclusion/Exclusion Criteria	See Section 3.0 for a complete list of inclusion and exclusion criteria
Description of Study Intervention:	HD-tACS will be used to deliver current (active vs. sham) to the electrodes to generate tACS most closely approximate endogenous neural activity. Participants will be fitted using a montage consisting of 5-9 electrodes placed over the right frontal and temporal scalp.
Duration of Study	approximately 6 weeks
Statistical Methodology	Aim 1: We will compare the percentage of participants requesting to discontinue the session and the number of mild and severe adverse events reported during and following the tACS vs. sham procedure using Bayes factors (BF). Aim 2: EEG data preprocessing and spectral analyses will be conducted using custom MATLAB scripts and EEGLAB following
	the general methods described in 11 150 5 published work.

STUDY SYNOPSIS

STUDY SCHEMA

1.0 BACKGROUND AND RATIONALE

1.1 Disease Background

Bipolar disorder (BD) is an impairing neuropsychiatric condition with high rates of relapse, morbidity, and mortality. Treatment of BD is challenging due to its complex clinical presentations and variable response to traditional pharmacologic treatments across individuals. Effective, personalized interventions are severely hindered by our lack of mechanistic insight of the disorder.

1.2 Study Agent(s) Background and Associated Known Toxicities

Recent groundbreaking work showed that transcranial alternating current stimulation (tACS), a noninvasive neuromodulation, can be programmed such that its wave patterns mimic natural theta-gamma coupling, a critical neural mechanism of cognitive control^{4,16}. Critically, applying frontal tACS targeting individualized peak theta/gamma coupling frequencies is able to enhance theta-gamma coupling and improve cognitive control performance among healthy non-psychiatric participants. These findings provide support for tACS's ability to modulate the neural underpinning of cognitive control in humans. This study will pursue critical next step towards realizing this potential therapy by demonstrating both feasibility (safety and tolerability) and efficacy of personalized tACS in engaging the neural target of affective cognitive control-related neural synchrony in BD patients.

1.3 Rationale

A growing body of research suggests that deficient cognitive control, the ability to modulate cognitive and emotional processes in order to optimize behavior and enhance adaptation with respect to the current context, may be a key mechanism contributing to these characteristics of BD. Specifically, behavioral studies strongly indicate that cognitive control, expressed as response inhibition, is impaired in BD¹ and associated with impulsivity and illness outcome.^{2,3} Therefore, understanding and leveraging the neural underpinnings of cognitive control is a promising avenue to developing neurobiologically-informed and precise treatments that target the underlying network dysfunction.

We have shown in a series of EEG studies that frontal theta-band (4-8 Hz) neural oscillatory activity and phase-amplitude coupling with gamma (30-60 Hz) activity are reduced in bipolar disorder during socioemotional processes requiring cognitive control. This provides support that theta-gamma coupling is a promising neural target to engage for BD. Recent groundbreaking work showed that transcranial alternating current stimulation (tACS), a non-invasive neuromodulation, can be programmed such that its wave patterns mimic natural theta-gamma coupling, a critical neural mechanism of cognitive control. Critically, applying frontal tACS targeting individualized peak theta/gamma coupling frequencies is able to enhance theta-gamma coupling and improve cognitive control performance among healthy non-psychiatric participants. These findings provide support for tACS's ability to modulate the neural underpinning of cognitive control in humans. This study will pursue critical next step towards realizing this potential therapy by demonstrating both feasibility (safety and tolerability) and efficacy of personalized tACS in engaging the neural target of affective cognitive control-related neural synchrony in BD patients.

1.4 **Objective**

This project will provide a critical proof of concept that personalized tACS is feasible and effective in engaging the neural target of theta-gamma coupling in BD patients, and importantly, helping them to

regain cognitive control. The ultimate goal of this research is to make this innovative and customizable treatment modality widely accessible for individuals living with BD.

2.0 STUDY DESIGN, AIMS AND OUTCOME MEASURES

The randomized, double-blind, sham-controlled, cross-over study will involve three sessions. The first session will involve a clinical interview, questionnaires, and EEG recording during a computerized task. The second and third sessions will involve tACS brain stimulation (or placebo stimulation) during a computerized task and EEG recording. Participant's psychiatric phenotypes and functioning will be dimensionally characterized. Affective cognitive control in bipolar disorder will be assessed using the Emotion Go-NoGo Task.

Aim #1: Evaluate the feasibility and acceptance of tACS among bipolar patients. Neuromodulation studies typically use dropout rate and reported adverse events as measures of acceptability and tolerability, respectively¹⁰. We will compare the percentage of participants requesting to discontinue the session and the severity of side effects reported following the tACS vs. sham procedure using Bayes factors (BF).

Intervention: One-session tACS

Primary outcome measure 1: Severity of side effects reported at end of stimulation session. This is calculated by summing the severity score of items (0-4) that are rated by the participant as related to stimulation (ratings of 3=probable or 4=definite) on the Stimulation Side Effects Questionnaire. **Primary outcome measure 2**: Withdrawal during or after the stimulation session.

Aim #2: Estimate the preliminary effects of personalized tACS on theta-gamma phase-amplitude coupling (PAC) and cognitive control behavior in BD.

Intervention: One-session tACS

Primary outcome measure 3: Accuracy signal detection theory metric sensitivity (d') derived from the behavioral responses to Go and NoGo trials on the cognitive control task.

Primary outcome measure 4: Accuracy signal detection theory metric response bias (β) derived from the behavioral responses to Go and NoGo trials on the cognitive control task.

Primary outcome measure 5: Reaction time (millisecond) of Go trials on the cognitive control task. **Primary outcome measure 6**: Theta-gamma PAC (Kullback-Leibler Modulation Index) during the rest EEG blocks interleaved between stimulation blocks.

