Previous literature suggests that participants are sensitive to stimulation until the sensory neurons in the skin acclimate to the stimulation. Thus, we will use sham stimulation as an active control condition. We will inform our participants that they will sense the stimulation in the skin but will acclimate to the stimulation soon after it begins. They will be informed that they will receive two version of the stimulation, to facilitate blinding in case the participant does not acclimate to the stimulation. For sham, a genuine cross-frequency waveform will be delivered at maximum strength for 12 s, followed by a ramp-down. The ramp-up and ramp-down during the sham stimulation is designed to mimic the feeling of acclimation that is experienced with verum stimulation due to sensory adaptation. Published data from Consultant [name]'s lab indicate that this procedure provides sufficient participant blinding to the condition⁴.

6) Cognitive Control Task (Emotion Go-NoGo Task)

Participants will engage in an Emotion Go-NoGo task to activate affective cognitive control during the baseline EEG as well as the stimulation sessions. In this task, participants view facial images exhibiting different emotions (neutral, happy, sad, or angry). For each face (150 ms), they are to press a button within 1500 ms if the face expresses the target emotion (Go trials; 80%) and withhold the response if the face expresses the distractor emotion (NoGo trials; 20%); the pairing of target and distractor emotions vary across blocks. The task includes a total of 640 trials, divided into 8 blocks of 80 trials each. Half (4) of the blocks include original face images (Easy condition), and the other half (4) include visually degraded images (Difficult condition). The two difficulty conditions are presented in alternating order (counter-balanced across participants). Accuracy (particularly on NoGo trials) and reaction time (on Go trials) will be used to index cognitive control behavior as outcome measures. [*Note: the timing and trial parameters of the actual task may be modified slightly depending on initial testing results].

- 7) *Stimulation Side Effects Questionnaire*. Participants will complete this questionnaire regarding their experience following each stimulation session. They will also be asked to rate how much the stimulation improved cognitive performance as well as if they experienced any side effects (e.g., headache, neck pain, tingling).

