Pleasant vs Neutral), and a grand total of 600 trials. Performance feedback will be provided and the stimuli presentation time will be adjusted based on performance after each block (e.g., if performance is above 90%, a 40ms shorter presentation time will be used in the next block) to ensure adequate number of errors and consistency in performance across participants within each part. Actual presentation and interval time may differ slightly in implementation from that described above. Estimated to take ~40 minutes. This task is designed to assess error and response monitoring within emotional contexts, which has been shown to be different from monitoring in other contexts, such as emotionally neutral context using arrows. Accuracy and reaction time will be used to index cognitive control behavior as outcome measures. EEG recorded during the Emotional Flanker task will be used to assess neurological indicators of attention control. [*Note: the timing and trial parameters of the actual task may be modified slightly depending on initial testing results. In order to reduce subject burden, experimenters may shorten the task and drop the display of pictures (neutral and valenced), using simple arrow cues instead to indicate a right or left button press].

Follow-up Phone Call (~ 5-10 min)

Approximately 4 weeks (+/- \sim 7 days) following the completion of Session 3, research staff will call to administer the Stimulation Side Effect Questionnaire as a final safety check and evaluate for any other possible side effects.

Stopping Rules

If a participant reports intolerable discomfort during the tACS procedure, the session will be discontinued. Immediately after each stimulation session ends, participants will complete a tACS side effects questionnaire. A study team member will review the responses and will immediately consult the PI if a participant reports a high (3) to very high (4) rating for any of the side effects rated to be related to the stimulation (4=probable or 5=definite). Subjects may also be withdrawn by the investigator when continued participation would present an unacceptable risk (e.g., worsening symptoms, suicidal thoughts, etc.).

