7.0 STATISTICAL CONSIDERATIONS

Aim 1 - Acceptability and Tolerability. Neuromodulation studies typically use dropout rate and reported adverse events as measures of acceptability and tolerability, respectively.¹² We will compare the percentage of participants requesting to discontinue the session and the severity of side effects reported following the tACS vs. sham procedure using Bayes factors (BF).

Aim 2 - tACS Effects on Neural Synchrony and Cognitive Control Behavior. EEG data preprocessing and spectral analyses will be conducted using custom MATLAB scripts and EEGLAB following the general methods described in **PI [name]**'s published work.⁷ Briefly, data will be downsampled to 500 Hz, filtered (0.1 – 100 Hz), re-referenced to common average, segmented into short epochs (for task data, -400 to 1800 ms time-locked to onset of stimuli; for rest data, 2 s epochs), applied independent component analysis to reject non-neural artifacts, baseline adjusted, followed by automatic artifact rejection of epochs containing voltage exceeding ±100 μ V. Data will be mirrored on both ends to minimize edge artifacts, applied Morlet wavelet convolution to extract power of different frequencies from 2 to 60 Hz. Theta-gamma PAC will be computed using the Kullback-Leibler Modulation Index (KLMI)⁸ implemented in the PAC Tools plugin for EEGLAB.⁹ Neural synchrony (theta-gamma PAC) during the rest EEG blocks and cognitive control performance (sensitivity d', response bias β , and reaction time on the Emotion Go-NoGo task) will be analyzed in separate repeated-measures ANCOVAs, with stimulation (tACS, sham) as within-subjects factor.

Potential Problems & Alternative Strategies

Participants Dropout. The study design entails each participant completing all 3 sessions. Our experience of conducting multiple-session neuromodulation studies suggests that average dropout rate for each subsequent session is 10-15%. We will enroll 30 participants to ensure that at least 20 participants will complete the study even with an overall dropout of 30%.

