Risks associated with completing the EEG:

(4) Discomfort or anxiety with EEG (infrequent) - The electrode application procedure involves putting gel on your head to help the wires measure brain signals. The gel will seem wet, which some people find slightly uncomfortable. There is also a minor risk of discomfort or anxiety/panic from being in the confined space for the EEG measurement.

Minimization of Risk: Participants can check the EEG measurement equipment and room to check if they will feel comfortable before agreeing to participate. They are also free to stop the study at any time if they become too uncomfortable.

(5) Risk of boredom, fatigue, or discomfort (likely) - It is possible that participants will become fatigued, frustrated, or uncomfortable.

Minimization of Risk: Participants are reminded during the study that they may choose to take a break or terminate participation at any time throughout the study.

Risk associated with tACS:

(6) Risk of Injury and Discomfort (mild and temporary) - The side effects of tACS are mild and transient; the participant may report mild tingling, burning, or itching under the electrode sites. *Minimization of risk:*

- To monitor mild side effects, we will be administering a stimulation questionnaire after each stimulation session to determine whether these effects were experienced and at what intensity.
- Research personnel present during these sessions will also check in with the participant periodically during the stimulation to see whether they are comfortable. If participant is experiencing severe discomfort (as determined by the questionnaire or by self-report), the stimulation will be stopped immediately.

If procedure becomes intolerable for the participant, the stimulation will be stopped. They may request a break from the procedures and/or may decline to answer any questions that make them feel uncomfortable.

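### Primary outcome 1 counts only side effects that participants attribute to stimulation, and no all-item severity comparison is planned to show whether the tolerability result depends on that filter

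*Combined protocol and SAP*

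**What the plan says.** Section 2.0 builds primary outcome 1 from the Stimulation Side Effects Questionnaire by "summing the severity score of items (0-4) that are rated by the participant as related to stimulation", and defines related as "ratings of 3=probable or 4=definite". Section 7.0 (Aim 1) then compares "the severity of side effects reported following the tACS vs. sham procedure using Bayes factors (BF"). It mentions no sum over all items, and gives no prior, model or threshold for the Bayes factor.

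Three other places bear on the point:

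- **Relatedness codes.** The stopping rules in section 5.2 use the same questionnaire but refer to side effects "rated to be related to the stimulation (4=probable or 5=definite"). These numbers differ from those in section 2.0.
- **Synopsis.** The statistical methodology row describes the Aim 1 comparison as "the number of mild and severe adverse events reported during and following the tACS vs. sham procedure". That is a count with no relatedness filter, not a severity sum.
- **Adverse-event recording.** Section 6.1 has all adverse events recorded whatever their assessed relationship to the procedure, but section 7.0 plans no analysis of them.

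**The concern.** Randomised order and a within-person sham session already answer the causal question. Whatever the cap, the task and the visit produce should appear in both sessions and cancel in the comparison. Asking the participant to judge causation as well puts a second, subjective filter on the outcome. It could act in two ways.

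1. **Dilution.** The questionnaire asks "if they experienced any side effects (e.g., headache, neck pain, tingling"), and it is completed after a 640-trial task under an EEG cap. Section 9.2.2 lists fatigue and discomfort among the EEG risks and rates them likely: "It is possible that participants will become fatigued, frustrated, or uncomfortable". A participant who blames the session for a headache that the current caused removes it from the score.
2. **Attribution that follows the condition.** Active current runs until the task ends, whereas sham has 12 s at full strength and then ramps down. Section 5.2 tells participants to expect two versions of the stimulation "to facilitate blinding in case the participant does not acclimate to the stimulation". If some participants sense which session is active, they may attribute the same symptoms more readily in that session.

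The stake is how the tolerability primary is read. Dilution would favour a conclusion of no difference from sham, and condition-dependent attribution would count against tACS. The filtered score alone cannot show whether either is at work.

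**Working it through.** **The plan's own figure.** No power or sample-size figure is given for primary outcome 1. The only one (section 7.0) is for Aim 2: N = 20, f = 0.21, correlation 0.8, alpha .05, two conditions. The noncentrality is 0.21² × 20 × 2 / (1 − 0.8) = 8.82, and with 1 and 19 degrees of freedom power is 0.804, which matches the stated 80%. It has no bearing on this point.

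**Inputs for the checks below.** From the documents: the filter, the 0–4 item scale and 20 completers. Everything else is assumed, because the documents give no item count, symptom rates, attribution rates or guess rates. The questionnaire itself is not included.

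**Check 1: dilution.** Let D be the true difference in all-item severity and q the share of severity rated probable or definite, the same in both sessions. The filtered difference is q × D. With means of 6 on tACS and 4 on sham, D = 2.0:

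- q = 0.75: 1.5
- q = 0.50: 1.0
- q = 0.25: 0.5

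The shrinkage is 1 − q, so it only restates the assumption about q.

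**Check 2: attribution that follows a guess.** Let true severity be M = 4 in both sessions, c the proportion guessing correctly, and a and s the attribution rates after guessing active and sham. The filtered difference is M × (2c − 1) × (a − s):

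- c = 0.5: 0, whatever a and s are
- c = 0.7, a = 0.6, s = 0.4: 4 × 0.4 × 0.2 = 0.32
- c = 0.7, a = 0.7, s = 0.3: 4 × 0.4 × 0.4 = 0.64
- c = 0.9, a = 0.7, s = 0.3: 4 × 0.8 × 0.4 = 1.28

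The all-item difference is 0 throughout, but only because severity is fixed at 4 whatever is guessed.

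**Check 3: signal against noise.** Raw points are not enough, since the filter also removes background symptoms. Assume ten independent items scoring 2 when present. Eight are background items (20% in both sessions) and two are stimulation items (20% on sham, 45% on tACS). Let A and B be the attribution rates for stimulation and background items. An item that counts with probability p has variance 4p(1 − p). The mean difference is 2 × 2 × A × 0.25 = A. The variance of the paired difference is 16 × 4(0.2B)(1 − 0.2B) + 2 × [4(0.45A)(1 − 0.45A) + 4(0.2A)(1 − 0.2A)]. For all items, A = B = 1, which gives 10.24 + 3.26 = 13.50.

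Power is for 20 pairs and a two-sided 5% paired t-test (noncentral t, 19 degrees of freedom), a stand-in for the unspecified Bayes factor:

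| Score | A / B | Mean difference | Variance | Difference / SD | Power |
|---|---|---|---|---|---|
| All items | – | 1.00 | 13.50 | 0.272 | 0.21 |
| Filtered | 80% / 10% | 0.80 | 4.17 | 0.392 | 0.38 |
| Filtered | 60% / 20% | 0.60 | 4.88 | 0.272 | 0.21 |
| Filtered | 60% / 30% | 0.60 | 6.03 | 0.244 | 0.18 |
| Filtered | 40% / 40% | 0.40 | 6.48 | 0.157 | 0.10 |

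Simulation of the same set-up agrees to within about 0.01. The filter helps when participants separate stimulation effects from background well, and hurts when they do not.

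**Check 4: relatedness codes.** Section 2.0 takes 3 and 4 as probable and definite; section 5.2 takes 4 and 5. If the form follows section 5.2, selecting 3 and 4 would admit the category below probable and drop definite. Which items enter the filtered score is therefore uncertain. The all-item sum does not use these codes.

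**The case against.** The strongest reply is that the filter is a defensible, pre-specified choice. Aim 1 concerns feasibility and acceptance, and the severity of effects that patients themselves ascribe to stimulation is a reasonable measure of that. Nothing in the documents shows under-attribution. A questionnaire about the stimulation experience that names headache and neck pain might equally prompt over-attribution. The tACS effects listed in section 9.2.2 (tingling, burning, itching under the electrodes) are easy to attribute, and fatigue appears only under EEG risks. Check 3 shows that the filter can improve precision. All of this stands.

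The second mechanism is also limited. It needs better-than-chance guessing and attribution that follows the guess. Section 5.2 has safeguards: ramping, a 12 s full-strength sham, the two-versions wording and cited blinding data. A participant who senses the condition might also report higher severity, so an all-item sum does not remove expectation effects. These points stand too, although no blinding check within this trial is described.

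Unfiltered information also exists: adverse events are recorded regardless of relationship (section 6.1), and the synopsis names an unfiltered count. This answers the point only in part. The count is a different measure, is absent from sections 2.0 and 7.0, and does not show what the severity sum would be without the filter.

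**Conclusion.** The point holds as a worthwhile, inexpensive improvement. The tolerability primary rests on a participant judgement that the sham comparison makes unnecessary, and no planned severity analysis shows whether the result depends on it. The filter may dilute a real difference, may create one, or may sharpen the contrast; direction and size cannot be determined from the documents. The ranges above (2.0 points falling to 0.5–1.5, a null reading 0.32–1.28, power of 0.10–0.38 against 0.21) are hypothetical and rest wholly on assumed rates.

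A reader might infer more: that real tACS effects will be lost, or that the outcome is tilted toward a favourable result. The documents do not support either. They contain no attribution data, condition-dependent attribution would work against tACS, and any percentage loss quoted would merely be one minus the assumed attribution rate. Nor do they support the view that an all-item sum is the unbiased answer, because it shares any expectation effect on reported severity.

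The conflict in relatedness codes and the mismatch between the synopsis and sections 2.0 and 7.0 need no assumptions. Both can be read directly from the text.

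**What to change.** - Keep the filtered score. Beside it, pre-specify the sum of severity over all side-effect items on the questionnaire regardless of rated relatedness. Compare it between tACS and sham with the same Bayes factor (same model and prior) and report both.
- State that tolerability will be described as similar to sham without qualification only if the two analyses agree. If they differ, report that the result depends on attribution.
- Specify this before the data are seen. Under section 4.2 the data analyst knows the assignment, so an all-item analysis chosen later would carry little weight.
- Reconcile the relatedness codes in sections 2.0 and 5.2 with the form in use, and define the filtered score by category name as well as number.
- Reconcile the synopsis adverse-event count with the severity measure in sections 2.0 and 7.0.

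Cost: one more analysis of data already collected, plus text corrections. The all-item sum carries more background symptoms and may be noisier, and it does not remove expectation effects on reported severity.

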6.0 ADVERSE EVENTS

6.1 Adverse Event Reporting Requirements

Adverse event (AE) monitoring and reporting is a routine part of every clinical trial and is done to ensure the safety of subjects enrolled in the studies as well as those who will enroll in future studies using similar agents. Data on adverse events will be collected after Sessions 2 and 3 through 30 days after study completion. Any serious adverse event that occurs more than 30 days after the last study

Session and is considered related to the study procedure must also be reported. Serious Adverse Events (SAEs) will continue to be followed until:

- Resolution or the symptoms or signs that constitute the serious adverse event return to baseline.
- There is satisfactory explanation other than the study procedure for the changes observed; or
 Death.

The investigator is responsible for the detection, documentation, grading, and assignment of attribution of events meeting the criteria and definition of an AE or SAE. The definitions of AEs and SAEs are given below. It is the responsibility of the PI to ensure that all staff involved in the trial is familiar with the content of this section.

Any medical condition or laboratory abnormality with an onset date before initial study procedure is considered to be pre-existing in nature. Any known pre-existing conditions that are ongoing at time of study entry should be considered medical history.

All events meeting the criteria and definition of an AE or SAE, as defined in Section 6.2, occurring from the initial study procedure through 30 days following the last Session must be recorded as an adverse event in the subject's source documents and on the clinical research file (CRF) regardless of frequency, severity (grade) or assessed relationship to the study procedure.

In addition to new events, any increase in the frequency or severity (i.e., toxicity grade) of a preexisting condition that occurs after the subject begins study procedure is also considered an adverse event. Review of AE and SAE data will be performed and documented on a routine basis by the study team and the PI during weekly study meetings.

6.2 **Definitions**

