6.3.2 Attribution of the AE

The investigator or co-investigator is responsible for assignment of attribution. Definite – The AE is clearly related to the study treatment/intervention. Probable – The AE is likely related to the study treatment/intervention. Possible – The AE may be related to the study treatment/intervention. Unlikely – The AE is doubtfully related to the study treatment/intervention. Unrelated – The AE is clearly NOT related to the study treatment/intervention.

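### The tolerability primary outcome and the PI-consultation trigger give different numeric codes to the same relatedness labels on one questionnaire

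*Combined protocol and SAP*

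**What the plan says.** Section 2.0 builds primary outcome measure 1 by "summing the severity score of items (0-4") over the items "rated by the participant as related to stimulation (ratings of 3=probable or 4=definite") on the Stimulation Side Effects Questionnaire. Sections 2.0 and 7.0 compare side-effect severity between tACS and sham with Bayes factors.

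The Stopping Rules in Section 5.2 have a team member read the responses after each stimulation session. That person "will immediately consult the PI if a participant reports a high (3) to very high (4) rating for any of the side effects" that the participant attributes to stimulation, and the rule describes these as "side effects rated to be related to the stimulation (4=probable or 5=definite").

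On the instrument, Section 5.2 item 7 says: "Participants will complete this questionnaire regarding their experience following each stimulation session". The assessment list in Section 5.1 and the schedule in Section 5.4 each show a single side-effects questionnaire. The response scale of that form does not appear in the documents.

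**The concern.** The two rules attach different numbers to the same two words. *Probable* is 3 in one and 4 in the other; *definite* is 4 in one and 5 in the other. With one form there is one key, so both number sets cannot be right. The pattern is what a one-point shift between a 0-to-4 and a 1-to-5 coding would produce.

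Both rules are operative. One defines the tolerability outcome for Aim 1. The other decides when the PI hears at once about a marked side effect. Section 8.3 says questionnaire data are entered largely by electronic capture. If relatedness is stored as a number, a script written from Section 2.0 would run without complaint on either coding, because 3 and 4 are valid values in both. Section 4.2 also leaves the PI and the data analyst unblinded, so settling the key after the data are in would be an unblinded decision about a primary outcome.

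**Working it through.** The plan gives no figure to reproduce here. The check has two parts: a comparison of the text, and a count of what each candidate key would do.

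**Same form?** The Stopping Rules use a slightly different name for the questionnaire. Its timing (after each stimulation session) and its respondent (the participant) match Section 5.2 item 7, and Sections 5.1 and 5.4 list only one such form. The severity codes also agree: 0 to 4 in Section 2.0, with 3 as high and 4 as very high in the Stopping Rules. The conflict is confined to relatedness.

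**Inputs**
- Severity: 0 to 4, five values (Section 2.0).
- Outcome rule as numbered: count the item if its relatedness code is 3 or 4 (Section 2.0).
- Trigger as numbered: severity 3 or 4 and relatedness code 4 or 5 (Section 5.2).
- Intended rule by label, the same in both places: related means *probable* or *definite*.
- Assumption: five ordered relatedness levels (*unrelated, unlikely, possible, probable, definite*). They are borrowed from the investigator attribution list in Section 6.3.2, which carries no numbers and where *possible* is defined as "The AE may be related to the study treatment/intervention".

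This gives 5 × 5 = 25 severity-by-relatedness cells per item. The trigger should fire in 2 × 2 = 4 of them (severity 3 or 4, *probable* or *definite*).

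| Form coding | Codes 3, 4 mean | Outcome cells wrong | Codes 4, 5 mean | Trigger fires in |
|---|---|---|---|---|
| 1 to 5 | possible, probable | 8 of 25 | probable, definite | 4 of 4 |
| 0 to 4 | probable, definite | 0 of 25 | definite, (no such code) | 2 of 4 |

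The 8 wrong cells on a 1-to-5 form are severity 1, 2, 3 and 4 rated *definite* (scored 0 instead of the severity: 4 cells) and severity 1, 2, 3 and 4 rated *possible* (counted instead of 0: 4 cells). The error for one item therefore runs from −4 to +4. The 2 trigger cells missed on a 0-to-4 form are severity 3 and severity 4 rated *probable*.

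**Session score on a 1-to-5 form**

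error = (sum of severity over *possible* items) − (sum of severity over *definite* items)

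Take a hypothetical participant with three items: severity 3 *probable*, severity 4 *definite*, severity 2 *possible*.
- By label: 3 + 4 = 7.
- By codes 3 and 4 on a 0-to-4 form: 3 + 4 = 7.
- By codes 3 and 4 on a 1-to-5 form: 3 + 2 = 5. The error is 2 − 4 = −2.

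**Effect on the contrast.** The error in the tACS minus sham difference is the session error under tACS minus the session error under sham. Each can be positive or negative, so the sign of the net bias is not fixed. The documents do not say how often each cell occurs.

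**The case against.** The best reply is that the rule is not really ambiguous. Each number is printed next to its label, the labels agree, and no document shows staff or a script working from bare numbers. Someone scoring by label makes no error under any key. That stands, and it is why the consequences are stated conditionally.

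The form's scale is also unseen, and five levels is an assumption. A four-level form coded 1 to 4 and ending in *probable* and *definite* would fit Section 2.0 and leave the outcome correct. That is true, but the trigger would then again catch only *definite* items, so one rule would still be wrong. The 25-cell count lists logical possibilities; it does not estimate how often an error would occur.

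On safety, other protections use no relatedness code. Sessions end for intolerable discomfort (Section 5.2), stimulation stops for severe discomfort (Section 9.2.2), serious events reach the PI within one business day whatever their attribution (Section 6.4), and adverse event data are reviewed "by the study team and the PI during weekly study meetings" (Section 6.1). A missed trigger would delay the PI's knowledge of a high-severity *probable* effect; it would not remove it. A reviewer might also notice that code 5 is absent from the form.

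These points limit the weight of the finding. They do not reconcile the two sections.

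**Conclusion.** The concern holds and should be fixed. The mismatch is certain from the text: at least one of the two numeric rules is wrong for the single listed questionnaire. Which one cannot be settled from the documents.

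The impact rests on two assumptions: five ordered relatedness levels, and literal use of the numbers. Under them, either primary outcome 1 is wrong in 8 of 25 cells per item (1-to-5 form), or the trigger misses 2 of its 4 intended cells (0-to-4 form). If the labels govern, neither error occurs. Confidence is high for the inconsistency. The documents do not support a figure for how much the tACS versus sham result would move, or in which direction.

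**What to change.** Check the relatedness coding on the printed questionnaire. Define a related side effect by label, *probable* or *definite*, and state one numeric key for the form. Use that key in primary outcome measure 1 (Section 2.0), in the Stopping Rules (Section 5.2) and in any scoring script, and store the label alongside the number. Do this before outcome data are analysed, since the PI and analyst know the assignment.

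The cost is protocol wording in two places and a check of any script. No new data are needed. If item-level ratings have been kept, which is an assumption, scores already computed can be redone once the key is confirmed.
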